7.8.2 Withdrawal from Study

The Investigator may withdraw subjects from the study for many reasons, including but not limited to the following:

- Subject noncompliance (e.g., did not follow instructions, took disallowed medications)
- Subject lost to follow-up (section 7.7)

Clinical Protocol

A Prospective, Multi-center, Study to Evaluate the Safety and Effectiveness of REAL INTELLIGENCE™ CORI™ in unicondylar knee arthroplasty (UKA) and total knee arthroplasty (TKA) procedures

Study Number: CORI.2019.07

Version: 6.0, 15/Jan/2024

Page: 37 of 122

- The Investigator or the Sponsor stop the study for any reason and decides to withdraw subject(s) from the study
- Concurrent illness
- Adverse Events/Adverse Device Effects
- Any other significant reason identified by the Investigator

For each case, the information will be recorded in the subject's source document and the electronic Case Report Form (eCRF), detailing circumstances leading to the withdrawal.

Subjects who drop out or are withdrawn will not be re-entered into the study at a later date.

If at any point during the study, the unicondylar or total knee prosthesis needs to be revised for any reason the following will apply: Subjects shall continue to have follow-up visits in order to monitor the subject's health status. Potential data following the revision surgery will not be included as study data but presented separately as safety data.

For minor revisions, where not the whole knee implant system is replaced (e.g. replacement of inserts) the subject shall continue with the study specific schedule and data will be presented.

7.8.3 Subject's Withdrawal of Consent to Participate in Study

Study participation is voluntary, and subjects may withdraw at any point during the study without giving their reason for doing so. Where subjects withdraw consent, the Investigator should make a reasonable effort to ascertain the reason(s), while fully respecting the subject's privacy. The reason for withdrawal will be recorded in the CRF and source documents.

7.8.4 Use of Data Following Withdrawal

In cases where the subject withdraws consent, the data collected up to the point of withdrawal may be used, but no additional data for that subject may be collected.

7.9 Subject Reimbursement and Incentives

Subjects will be reimbursed for the costs of taking part in the study in compliance with local regulations. These costs will only cover study-specific activities or visits including time, travel, parking and inconvenience and will not cover activities or visits associated with the subject's standard clinical care. Payments to the subject will be proportionate to the time and expense involved in study participation and not so large as to unduly encourage the subjects to participate or affect the subject's ability to withdraw prematurely from the study. All arrangements for reimbursement payments to subjects will be approved by the IRB/IEC and/or local site authority as required.

Clinical Protocol

A Prospective, Multi-center, Study to Evaluate the Safety and Effectiveness of REAL INTELLIGENCE™ CORI™ in unicondylar knee arthroplasty (UKA) and total knee arthroplasty (TKA) procedures

Study Number: CORI.2019.07

Version: 6.0, 15/Jan/2024

Page: 38 of 122

8. STUDY DESIGN

8.1 Study Design

This study is a prospective, multi-center, non-randomized, non-blinded follow-up study to evaluate the use of CORI Robotics in UKA and TKA procedures in achieving post-operative leg alignment. Up to 8 sites will participate within Europe, UK, India and the US.

Subjects will be enrolled in one of two (2) groups based on medical indication and general practice at the site, as shown in Table 8-1. All subjects are treated with knee arthroplasty with the use of the CORI Robotics and a Smith+Nephew Knee Implant System based local regulatory status and medical indication and general practice at the site (see Table 6-1 S+N Implant Systems available with CORI Robotics for this study).

Table 8-1 Overview of Study Groups

Group	Surgical Technique	Knee Implant system	Number of Subjects
Primary UKA	CORI Robotics	Smith+Nephew UKA Implant System	40
Primary TKA	CORI Robotics	Smith+Nephew TKA Implant System	40

The study is expected to enroll all subjects within a 24 month timeframe. Subjects will be followed-up for a time period of 12 months after surgery.

This study is being conducted in parallel to 2 randomized-controlled studies in China titled: "A Prospective, Multi-center, randomized-controlled Study to Evaluate the Safety and Effectiveness of REAL INTELLIGENCE™ CORI™ in unicondylar knee arthroplasty (UKA) procedure" (Protocol ID: CORI.2019.06) and "A Prospective, Multi-center, Randomized Controlled Study to Evaluate the Safety and Effectiveness of the REAL INTELLIGENCE™ CORI™ in total knee arthroplasty (TKA) Procedure" (Protocol ID: CORI.2020.08). The study data may be combined for analysis to meet the requirements for regulatory approval of the CORI Robotics by the National Medical Products Administration (NMPA) in China. Further details are described in Section 10 Statistical Design and the Statistical Analysis Plan (SAP).

Figure 8-1 details the different steps of study conduct from screening to enrollment and follow-up.

Subjects may be assigned a subject ID, but then not enrolled in the study (e.g. did not receive the study device or decided not to participate in the study).

Clinical Protocol

[figure not shown]
A Prospective, Multi-center, Study to Evaluate the Safety and Effectiveness of REAL INTELLIGENCE™ CORI™ in unicondylar knee arthroplasty (UKA) and total knee arthroplasty (TKA) procedures

Study Number: CORI.2019.07

Version: 6.0, 15/Jan/2024

Page: 39 of 122

Figure 8-1 Study Flowchart

The study design meets the needs of the aforementioned regulatory requirements and has been powered based on recent analyses from the NAVIO Surgical System. This study is designed to demonstrate superiority in the proportion of TKAs post-operatively defined as mechanically aligned against the reference proportion of 73.4% (53). The proportion of mechanically aligned TKAs using the NAVIO™ Surgical System from a recent analysis was estimated to be 92.1% (54). If this assumption holds for this study, then the enrollment of 36 knees for each of the two planned study groups (i.e. the CORI Robotics UKA and CORI Robotics TKA) for a total of 72 knees will individually provide approximately 80% power to show that the lower limit of the two-sided 95% confidence interval for the proportion of mechanically aligned TKAs is greater than that obtained from literature. To account for up to a 10% attrition rate in knees enrolled, 40 knees in each group (80 knees combined, 40 UKA and 40 TKA) will be enrolled in the study.

8.2 Data Management

This study utilizes a validated, 21 CFR Part 11 compliant, electronic data capture system. Access to the electronic data capture system is controlled through Smith and Nephew procedures.

A Data Management Plan (DMP) is written according to Smith and Nephew procedures containing details of the data management process. The following is a brief description of the key points detailed in this plan.

8.2.1 Data Review and Quality Assurance

Data will be transcribed from the data source to an electronic Case Report Form (eCRF). All data requested on the eCRFs are considered required. Data points not collected and/or recorded will be considered deviations unless otherwise specified.

Clinical Protocol

A Prospective, Multi-center, Study to Evaluate the Safety and Effectiveness of REAL INTELLIGENCE™ CORI™ in unicondylar knee arthroplasty (UKA) and total knee arthroplasty (TKA) procedures

Study Number: CORI.2019.07

Version: 6.0, 15/Jan/2024

Page: 40 of 122

Data collection is the responsibility of the clinical trial staff at the site under the supervision of the Principal Investigator. The Principal Investigator is responsible for ensuring the accuracy, completeness, legibility, and timeliness of the data reported. The Principal Investigator must provide his/her electronic signature on the appropriate eCRFs to be documented in compliance with local regulations. Changes to data previously submitted to the sponsor will require a new signature by the Investigator to acknowledge/approve the changes.

Visual and computer data review will be performed in line with Smith and Nephew procedures to identify possible data discrepancies. Manual and automatic queries will be created within the electronic data capture system and will be issued by Smith and Nephew to the site for appropriate response. Site staff are responsible for resolving all queries in the electronic data capture system.

8.2.2 Retention Period

All eCRFs will be archived once the study is completed and will be kept for a period of no less than five years after the later of the following dates: the date of which the study is terminated or completed or the date that the records are no longer required supporting marketing applications.

8.3 Study Endpoints

8.3.1 Primary Endpoint

The primary endpoint of this study is defined as the evaluation of the proportion of subjects achieving post-operative leg alignment at 6 weeks post-surgery. Achieved leg alignment is defined as $\pm 3^\circ$ from the subject's specific target.

This primary endpoint is aligned to the primary study objective of evaluating the CORI surgical system for UKA and TKA procedures in achieving post-operative leg alignment. Accuracy and alignment are two key variables in successful UKA and TKA procedures. These measures have been previously evaluated with the predicate NAVIO surgical system. The primary endpoint will support the continued evaluation of these variables for the CORI surgical system.

8.3.2 Secondary Endpoints

The following secondary endpoints have been defined for this study in order to evaluate the safety and performance of the CORI Robotics:

- Component Alignment 6 weeks post-surgery
- Radiographic assessment (Presence of radiolucent lines, osteolysis & implant migration) 12 months post-surgery
- 2011 Knee Society Score (KSS) at baseline, 6 weeks, 6 and 12 month post-surgery
- Oxford Knee Score (OKS) at baseline, 6 weeks, 6 and 12 month post-surgery
- Forgotten Joint Score (FJS) at 6 weeks, 6 and 12 month post-surgery

Clinical Protocol

A Prospective, Multi-center, Study to Evaluate the Safety and Effectiveness of REAL INTELLIGENCE™ CORI™ in unicondylar knee arthroplasty (UKA) and total knee arthroplasty (TKA) procedures

Study Number: CORI.2019.07

Version: 6.0, 15/Jan/2024

Page: 41 of 122

- Five-level EuroQol five-dimensional (EQ-5D-5L) VAS & index scores at baseline, 6 weeks, 6 and 12 month post-surgery

Secondary endpoints are aligned to the secondary study objectives of generating safety and performance evidence related to the use of the CORI surgical system. Assessing alignment, radiographic image assessment and patient-reported outcome measures (PROMS) are key variables in determining the success of UKA and TKA procedures. These endpoints have been previously evaluated with the predicate NAVIO surgical system and ongoing assessment of these secondary endpoints under this study will support safety and efficacy of these procedures performed with the CORI surgical system.

8.3.3 Other Endpoints

The following additional endpoints collected during surgery have been defined for this study:

- Leg alignment pre- and post-cementation
- Robotics System time as extracted from the Subject's CORI Robotics Case Report generated by the CORI Robotics Software.
- Cutting time of the robotic drill s extracted from the Subject's CORI Robotics Case Report, generated by the CORI Robotics Software.

8.3.4 Safety Endpoints

Safety endpoints include the collection of the following events:

- All adverse events (AEs) and complications occurring from the time of subject enrollment until study termination or study completion including intra-operative adverse events and complications.
- Device related re-intervention
- Device Deficiencies
- Knee implant revision rate

All AEs will be categorized in terms of seriousness and relatedness to the study device or to the surgical procedure (Adverse Events, Serious Adverse Events, Adverse Device Effects, Serious Adverse Device effects). All Serious Adverse Device Effects will be further categorized as Anticipated or Unanticipated. The definitions for each of these categories are based on ISO 14155. (Including hardware and instrumentation), complications, and revisions.

Clinical Protocol

A Prospective, Multi-center, Study to Evaluate the Safety and Effectiveness of REAL INTELLIGENCE™ CORI™ in unicondylar knee arthroplasty (UKA) and total knee arthroplasty (TKA) procedures

Study Number: CORI.2019.07

Version: 6.0, 15/Jan/2024

Page: 42 of 122

8.4 Methods Used to Minimize Bias and Maximize Validity

8.4.1 Multiple sites

Subjects will be enrolled at multiple sites, utilizing up to 8 sites in total for the study. This will reduce the effect of observer bias that might arise at any one investigational site as well as maximize the diversity of subjects treated.

8.4.2 Prospective Consecutive Enrolment

Consecutive enrollment will be utilized to enroll subjects who meet the inclusion/exclusion criteria.

8.4.3 Subject Attrition

The required sample size for the study includes adjustment for expected subject attrition.

8.4.4 Pre-specification of Statistical Analysis

The primary outcome measure has been pre-specified as well as the type of statistical analysis to be performed in order to evaluate this outcome. The details of the analysis will further be pre-specified in the Statistical Analysis Plan (SAP) so as minimize any threats to external validity and yield clinically relevant estimates of effects and precision.

9. STUDY PROCEDURES

9.1 Visits and Examinations

9.1.1 Summary

For a summary of the required procedures by visit, refer to the Study Schematic Table 9-1:

Clinical Protocol

A Prospective, Multi-center, Study to Evaluate the Safety and Effectiveness of REAL INTELLIGENCE™ CORI™ in unicondylar knee arthroplasty (UKA) and total knee arthroplasty (TKA) procedures

Study Number: CORI.2019.07

Version: 6.0, 15/Jan/2024

Page: 43 of 122

Table 9-1: Study Procedures by Visit

Schedule of events	Pre-Operative Data -90 to 0 days	Operative Data & Discharge Day 0 (+ up to 9 days) ⁴	6 weeks 42 ± 14 days	6 months ⁵ 185 ± 14 days	12 months 365 ± 30 days
Informed Consent	X				
Inclusion/Exclusion	X				
Demographics/ Medical History	X				
Concomitant Medication Update		X	X	X	X
Operative Data Collection		X			
Knee Implant Disposition		X			
CORI Robotics Case Report (Robotic System time & cutting time)		X			
Discharge Data Collection		X			
Leg alignment Long leg X-ray AP	X	(X) ¹	X		(X) ²
Standard Lateral X-ray		(X) ¹	X		X
Standard A/P X-ray					X
KSS	X		X	X	X
OKS	X		X	X	X
FJS			X	X	X
EQ-5D-5L	X		X	X	X
Safety Assessment		X	X	X	X
End of Study/Exit			(X) ³	(X) ³	(X) ³

¹ Post-operative standing weight bearing long leg X-rays (A/P & L) may be taken at discharge if standard of care.

² Only if standing weight bearing long leg A/P X-ray is taken as a standard of care at 12 months.

³ Exit form to be completed at the point of withdrawal if the study is not completed.

⁴ If any Pre-Operative data is collected on the day of surgery, it must be completed prior to the surgery occurring.

⁵ The 6 month visit may be conducted remotely

Clinical Protocol

A Prospective, Multi-center, Study to Evaluate the Safety and Effectiveness of REAL INTELLIGENCE™ CORI™ in unicondylar knee arthroplasty (UKA) and total knee arthroplasty (TKA) procedures

Study Number: CORI.2019.07

Version: 6.0, 15/Jan/2024

Page: 44 of 122

9.1.2 Screening/Preoperative Visit (-90 to 0 days)

1. Obtain written informed consent from the subject as detailed in Section 7.5. Any subject who signs an informed consent but fails to meet the entry criteria is considered to be a Screen Failure. Their demographic information must be captured in the appropriate electronic Case Report Form (eCRF) with the reason for screen failure specified.

----- **Do not proceed until consent has been obtained** -----

2. Obtain demographic information and medical history, including information on all concomitant medications/therapies.
3. Screen the subject for protocol inclusion/exclusion criteria.
4. The eCRF will assign the subject a study number. The subject identification log shall be completed accordingly.
5. Assign the subject a study number and instruct the subject on treatment procedures.
6. Collect radiographic images of the affected knee for evaluation of leg alignment (Standing weight bearing A/P long leg X-ray) (x-rays can be taken within 6 months of the surgery date)
7. Collect the KSS score objective measures (joint alignment, instability, motions & symptoms).
8. Have the subject complete the KSS score subject questions.
9. Have the subject complete the OKS patient-reported outcome measure
10. Have the subject complete the EQ-5D-5L patient-reported outcome measure.
11. Subjects will be instructed to return for the Operation Visit on a scheduled date.

9.1.3 Operation Visit & Discharge (Day 0 up to Day 9)

If any Pre-Operative data is collected on the day of surgery, it must be completed prior to the surgery occurring.

1. Check if there is any change in eligibility of the subject since the pre-operative visit. If the subject is no longer eligible, document as screening failure.
2. Query subject regarding any changes in general health and the use of concomitant medications/therapies.
3. Collect data on the surgical plan: Target Leg alignment as entered into the CORI Robotics.
4. Perform surgery and collect intra-operative data on the appropriate eCRF. This includes but is not limited to the following information:

Clinical Protocol

A Prospective, Multi-center, Study to Evaluate the Safety and Effectiveness of REAL INTELLIGENCE™ CORI™ in unicondylar knee arthroplasty (UKA) and total knee arthroplasty (TKA) procedures

Study Number: CORI.2019.07

Version: 6.0, 15/Jan/2024

Page: 45 of 122

- Knee Implant Disposition (recording of tibial baseplate, insert and femoral component name, reference & lot/batch number)
- Surgical data (e.g. duration, blood loss, surgical approach)
- Collect pre- (with the trial implant in place) and post cementation alignment with the use of CORI Robotics.
- Collect the Subject's CORI Robotics Case Report, generated CORI Robotics Software (Robotics System time, cutting time)

5. Complete discharge eCRF.
6. If any adverse device effects or device deficiencies are observed or reported, they must be recorded as instructed in Section 12 - Adverse Events and Device Deficiencies.
7. Instruct the subject on proper postoperative care/procedures, including any contraindicated treatments/medication(s).
8. Instruct the subject returning to the site for the next follow up visit 6 weeks (42 ± 14 days) after the surgery date.

9.1.4 Follow-up visits at 6 weeks (42 ± 14 days)

1. Query subject regarding any changes in general health and the use of concomitant medications/therapies.
2. If any adverse device effects or device deficiencies are observed or reported, they must be recorded as instructed in Section 12 - Adverse Events and Device Deficiencies.
3. Verify with the subject if any revision has occurred since the last visit. If any revision is observed or reported, it must be recorded as instructed in Section 12 - Adverse Events and Device Deficiencies.
4. Collect the KSS score objective measures (joint alignment, instability, motions & symptoms).
5. Have the subject complete the KSS score subject questions.
6. Have the subject complete the OKS patient-reported outcome measure
7. Have the subject complete the EQ-5D-5L patient-reported outcome measure.
8. Have the subject complete the FJS patient-reported outcome measure.
9. Collect the standing weight bearing long leg (A/P) and standard lateral (non-weight bearing) radiographic images of the affected knee. Review the images to complete the appropriate eCRF for leg alignment and component alignment.

Clinical Protocol

A Prospective, Multi-center, Study to Evaluate the Safety and Effectiveness of REAL INTELLIGENCE™ CORI™ in unicondylar knee arthroplasty (UKA) and total knee arthroplasty (TKA) procedures

Study Number: CORI.2019.07

Version: 6.0, 15/Jan/2024

Page: 46 of 122

10. Instruct the subject on follow-up procedures, including returning to the site for the next follow-up visit in 6 months (185 ± 14 days) after the surgery date or make arrangements for delivery of the 6 month PROMs by courier to the subject to be completed remotely.

9.1.5 6 months (185 ± 14 days) after surgery (phone call if remote)

1. Query subject regarding any changes in general health and the use of concomitant medications/therapies.
2. If any adverse device effects or device deficiencies are observed or reported, they must be recorded as instructed in Section 12 - Adverse Events and Device Deficiencies.
3. Verify with the subject if any revision has occurred since the last visit. If any revision is observed or reported, it must be recorded as instructed in Section 12 - Adverse Events and Device Deficiencies.
4. Collect the KSS score objective measures (joint alignment, instability, motions & symptoms) (if it is an on-site visit)
5. Have the subject complete the KSS score subject questions.
6. Have the subject complete the OKS patient-reported outcome measure
7. Have the subject complete the EQ-5D-5L patient-reported outcome measure.
8. Have the subject complete the FJS patient-reported outcome measure.
9. If the visit was remote arrange for courier to return the completed PROMs to site.
10. Instruct the subject on follow-up procedures, including returning to the site for the next follow-up visit 12 months (365 ± 30 days) after the surgery date.

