4.4.7 Safety Data Collection

All adverse device effects or device deficiencies will be categorised and reported as instructed in Section 12, Adverse Events and Device Deficiencies. During causality assessment activity (assessment of Related vs Unrelated) and expectancy assessment (assessment of Unanticipated vs Anticipated) clinical judgement shall be used and relevant documents, such as the IFU shall be consulted, as foreseeable serious adverse events and the potential risks are summarized there. The presence of confounding factors, such as concomitant medication/treatment, the natural history of the underlying disease, other concurrent illness or risk factors shall also be considered.

Clinical Protocol

A Prospective, Multi-center, Study to Evaluate the Safety and Effectiveness of REAL INTELLIGENCE™ CORI™ in unicondylar knee arthroplasty (UKA) and total knee arthroplasty (TKA) procedures

Study Number: CORI.2019.07

Version: 6.0, 15/Jan/2024

Page: 24 of 122

5.OBJECTIVE(S)

To evaluate the safety and effectiveness of REAL INTELLIGENCE™ CORI™ in UKA and TKA procedures.

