9.1.7 Unscheduled Visits

Unscheduled examinations related to the study knee may be conducted at the discretion of the Investigator with all obtained information recorded in the source documents and on the appropriate eCRF. If any adverse events or device deficiencies are observed or reported, they must be recorded as instructed in Section 12. - Adverse Events and Device Deficiencies. The subject should be scheduled to return for the next scheduled study visit within the acceptable time window.

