10.5 Safety Analyses

All safety analyses will be carried out separately for each of the groups (CORI Robotics UKA and CORI Robotics TKA groups) and overall as follows:

- The number of adverse events will be reported both overall and by seriousness, relationship to study device and anticipation.
- The number of subjects experiencing adverse events will be summarised both overall and by seriousness, relationship to study device and anticipation.
- An overall AE summary table that will summarize as number (n) and percentages (%), the overall incidence according to subjects with at least one AE; subjects with at least one AE by worst severity (mild, moderate, or severe); subjects with at least one AE by worst outcome (resolved, ongoing/unresolved, or death); subjects with an AE that led to study discontinuation) and; subjects with at least one AE by worse relatedness to device. Other events such as SAEs, ADEs, SADEs or UADEs will also be similarly summarized using the number (n) and percentages (%).
- Incidence of device-related re-interventions that occur on-study will be summarized as number (n) and percentages as well as by type.
- A listing of device deficiencies that occur on-study will be provided.
- Knee implant revision rate will be summarized as proportions with 95% CIs estimated using exact binomial methods.

All safety endpoints will be summarized using the SAF analysis population.

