12.3 Reporting procedures

AE of any kind and DD will be recorded in the applicable CRF and source notes to include the date of occurrence, treatment, and the details resolution. The Investigator will evaluate all AE for relationship to the device and procedure, seriousness, and severity (if applicable). DD will be evaluated for potential to cause SADE. The following timescales should be followed for the AE/DD information to be submitted/entered into the CRF and reported to the Sponsor or designee (see figure 12.2-1):

- ADE and DD – without unreasonable delay
- SAE, SADE, and DD with potential to cause SADE – immediately (i.e. within 24 hours of the investigator being informed about the event)
- All other events – according to usual timescales

In addition to inputting SAE and SADE information within 24 hours of being aware of the event, the investigator should email [contact] to alert the safety representative of the events existence and to clarify details if necessary.

For ADE and DD, date of occurrence, and details of the product/procedure related to the event will be included and where applicable, pictures taken of the device. The deficient product should be retained for return to S+N unless it is contaminated (e.g., used dressings must not be retained). Updates to submitted information will be recorded in the CRF according to the timescales above.

All adverse events will be reviewed by a medically qualified person appointed by the Sponsor to determine which, if any, meet criteria for expedited reporting to the regulatory authorities.

The investigator will inform the regulatory agency and IRB/IEC of adverse events as per the requirements listed below:

Unanticipated SADE's and DD's that could have led to SADE will be reported to IEC/IRB and regulatory authorities within 10 working days.

Clinical Protocol

A Prospective, Multi-center, Study to Evaluate the Safety and Effectiveness of REAL INTELLIGENCE™ CORI™ in unicondylar knee arthroplasty (UKA) and total knee arthroplasty (TKA) procedures

Study Number: CORI.2019.07

[figure not shown]
Version: 6.0, 15/Jan/2024

Page: 67 of 122

All other events will be reported on a periodic/annual basis.

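### The visit steps from surgery onward, and Section 4.4.7, name adverse device effects where the safety endpoint and the recording rule name all adverse events

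*Combined protocol and SAP*

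**What the plan says.** The narrow wording is in five places. Section 9.1.3 step 6 and step 2 of Sections 9.1.4, 9.1.5 and 9.1.6 each say "If any adverse device effects or device deficiencies are observed or reported, they must be recorded as instructed in Section 12". Section 4.4.7, the general statement on safety data collection, says "All adverse device effects or device deficiencies will be categorised and reported as instructed in Section 12".

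The broad wording is in the sections that set the endpoint, the analysis and the duty to record:

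- Section 8.3.4 defines the safety endpoint as "All adverse events (AEs) and complications occurring from the time of subject enrollment until study termination or study completion".
- Section 10.5 plans the analysis on that basis: "The number of adverse events will be reported both overall and by seriousness, relationship to study device and anticipation".
- Section 12.3, to which the visit steps refer, says "AE of any kind and DD will be recorded in the applicable CRF and source notes", and has the investigator judge relationship for all of them.
- Section 22.7 item 8a obliges the principal investigator to record every adverse event and every observed device deficiency, with an assessment.
- Section 9.1.7, for unscheduled visits, says "If any adverse events or device deficiencies are observed or reported, they must be recorded as instructed in Section 12".

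**The concern.** Section 9 is the part of a protocol that a coordinator follows at the visit. Its recording step is conditional: if an event of the named kind is seen, go to Section 12. The named kind is a related event. Read literally, the site decides on causality first, and an event judged unrelated never meets the condition that leads to Section 12. Section 12.3 has the opposite order: record the event, then assess its relationship.

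Safety is part of the secondary objective (Section 5.2), and Section 10.5 reports adverse events overall before splitting them by seriousness, relationship and anticipation. If sites differ in which instruction they follow, the overall figures would depend partly on site practice, and the unrelated category would be the one depleted.

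**Working it through.** No figure in the plan is in dispute, so the check is a comparison of text.

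**1. Is the visit wording really narrower?** Section 12.1.2 defines an adverse device effect as an adverse event related to use of the investigational device. It is therefore a subset of adverse events. Section 6.1.1 makes the robotic system, not the implant, the investigational product.

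**2. How much narrower?** Section 12.1.2 counts an event as related if a relationship to the product or the procedure is possible or definite, and as not related only if it is definitely unrelated. Table 12.1-1 likewise puts procedure-related events in the device-effect column. Under those definitions the events outside the visit wording are those judged definitely unrelated to both device and procedure. The opening sentence of 12.1.2 mentions the device alone, so a site reading only that sentence could apply a tighter test.

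**3. Which visits are affected?** The wording is in all four scheduled visits from surgery onward. The preoperative visit (9.1.2) has no safety-recording step, but Section 7.6 counts a subject as enrolled only once treated. The endpoint window therefore opens after that visit, and the four visits are all the scheduled visits within it.

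**4. Do other visit steps close the gap?** In part.

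| Element | Where | Effect |
|---|---|---|
| General-health query: "Query subject regarding any changes in general health and the use of concomitant medications/therapies" | 9.1.3 step 2; 9.1.4 to 9.1.6 step 1 | Brings unrelated events to light, but no step then says to record them as adverse events |
| Revision check | 9.1.4 to 9.1.6 step 3 | Any revision is recorded, whatever its cause |
| Safety Assessment row | Table 9-1, all four visits | Schedules an assessment without defining its scope |
| Concomitant medication and therapy entries | 9.1.8.1.2, 9.1.8.1.4 | For adverse event treatment, limited to device-related events and device deficiencies; fits a narrow reading |

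**5. Which way would omissions act?** Section 10.5 uses the safety population, which is all treated subjects, so the denominator does not change. Omitted events can only lower the numerator. With the planned 40 treated subjects per group, each subject whose only adverse event went unrecorded would lower that group's incidence by 1/40 = 2.5 percentage points, or 1/80 = 1.25 points for both groups together. A subject with another recorded event would still count as having one, and only the event count would fall. How many subjects might be affected cannot be derived: the documents give neither an expected adverse event rate nor an expected share of unrelated events.

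**The case against.** The strongest reply is that the protocol, read as a whole, leaves no doubt about what must be collected. Sections 12.3 and 22.7 item 8a require every adverse event. Section 12.1.5 has severity graded for every one. Table 12.1-1 has a column for events not related to the device, and Section 12.5.1 gives unrelated events their own follow-up rule, which presupposes that they are captured. The visit steps do not contain the word only and forbid nothing. All of this stands, and it reduces the point from a restriction on collection to a conflict of wording. It does not remove the conflict, because the visit step sends a site to Section 12 only when the event is already regarded as device-related.

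A reader might infer three stronger things, none of which the documents support:

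- **That the sponsor chose to collect device-related events alone.** The endpoint, analysis, reporting rule and investigator obligation all say otherwise.
- **That serious adverse events would be lost.** Section 12.3 requires them within 24 hours of the investigator being informed, with an alert by email, and this does not depend on the visit checklist.
- **That the sponsor would have no sight of unrelated events.** Section 12.3 provides for a sponsor-appointed medically qualified person to review all adverse events. An event never entered would escape that review, but the plan does not intend any to be left out.

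**Conclusion.** The point holds as an internal inconsistency, not as a design choice. Four visit sections and Section 4.4.7 have a narrower recording scope than the endpoint, the analysis, the reporting rule, the investigator obligation and the unscheduled-visit text. The plausible consequence is that some sites leave out adverse events they judge unrelated, chiefly non-serious events judged definitely unrelated to device and procedure. That could bias overall adverse event incidence downward and make it vary by site.

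This assumes that at least some sites work from the Section 9 steps rather than from Section 12. The case report form and its completion guidelines are not among the documents; if they prompt for all adverse events, the risk is smaller. The size cannot be estimated. The primary endpoint, the sample size and the analysis methods are unaffected.

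**What to change.** In Section 9.1.3 step 6, step 2 of Sections 9.1.4, 9.1.5 and 9.1.6, and Section 4.4.7, replace the reference to adverse device effects or device deficiencies with adverse events of any kind or device deficiencies. Add that relatedness is assessed after the event is recorded, as Section 12.3 already provides. This brings the visit steps into line with Sections 8.3.4, 9.1.7, 10.5, 12.3 and 22.7.

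The cost is a wording change in five places and a reminder to sites. Sites may enter somewhat more events, but they take on no duty that Section 12.3 does not already impose. It is best done while visits are still taking place, because unrecorded non-serious events may be hard to recover later.
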